5.11 Subject Withdrawal/Discontinuation Criteria

Subjects may withdraw consent at any time for any reason or be dropped from the trial at the discretion of the investigator should any untoward effect occur. In addition, a subject may be withdrawn by the investigator or the Sponsor if enrollment into the trial is inappropriate, the trial plan is violated, or for administrative and/or other safety reasons. Specific details regarding discontinuation or withdrawal are provided in Section 8.1.2 – Other Procedures.

A subject must be discontinued from the trial for any of the following reasons:

- The subject or legal representative (such as a parent or legal guardian) withdraws consent.
- Confirmed disease progression
 - Increase in $\geq 25\%$ from best response and/or lowest measurable value in
 - Serum M-component and/or (the absolute increase must be ≥ 0.5 g/dL)
 - Urine M-component and/or (the absolute increase must be ≥ 200 mg/24h)
 - Only in patients without measurable serum and urine M-protein levels: the difference between involved and uninvolved free light chains levels. The absolute increase must be > 10 mg/dl.
 - Bone marrow plasma cell percentage: the absolute % increase must be $\geq 10\%$
 - Definite development of new bone lesions or soft tissue plasmacytomas
 - Development of hypercalcemia (corrected serum calcium > 1 mg/dL higher than the upper limit of normal or > 11 mg/dL) that can be attributed solely to the plasma cell proliferative disorder
 - Rise in serum creatinine by 2 mg/dl or more and/or creatinine clearance > 40 ml/min, that can be attributed solely to the plasma cell proliferative disorder
 - Development of anemia with a hemoglobin 2 g/dl below the lower limit of normal

- Unacceptable adverse experiences as described in Section 5.7.1.2
- Intercurrent illness that prevents further administration of treatment
- Investigator's decision to withdraw the subject
- The subject has a confirmed positive serum pregnancy test
- Noncompliance with trial treatment or procedure requirements
- The subject is lost to follow-up
- Administrative reasons

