The End of Treatment and Follow-up visit procedures are listed in Section 7.0 (Study Calendar). After the end of treatment, each subject will be followed for 90 days for adverse event monitoring (serious adverse events will be collected for 90 days after the end of treatment as described in Section 7.0 (study calendar, adverse events/toxicity, footnotes ^{b,j}). Subjects who discontinue for reasons other than progressive disease will have post-treatment follow-up for disease status until disease progression, initiating a non-study cancer treatment, withdrawing consent or becoming lost to follow-up. After documented disease progression each subject will be followed by telephone for overall survival until death, withdrawal of consent, or the end of the study, whichever occurs first.

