6.2.1 Light chain only disease

- a) If patient does not have presence of "measurable" serum or urine M-protein (those are negative in electrophoresis), but has either a serum kappa or lambda FREE light chain of 10 mg/dL along with an abnormal kappa to lambda free light chain ratio, patient is considered to have "measurable" disease.
- b) The serum free light chain (FLC) assay is of particular use in monitoring response to therapy in patients who have oligo-secretory disease. When using this assay, it is important to note that the FLC levels vary considerably with changes in renal function and do not solely represent monoclonal elevations. Thus both the level of the involved and the uninvolved FLC isotype (i.e., the involved/uninvolved ratio or involved-uninvolved difference) should be considered in assessing response. The serum FLC assay should be used in assessing response only if the baseline serum and/or urine M proteins are not "measurable" by traditional criteria, and the baseline level of the involved FLC is 10mg/dL and clonal (abnormal ratio). Patients included on the study on the basis of FLC alone (i.e., no measurable serum/urine) should be the only ones who are evaluated using FLC response criteria. The others should follow usual criteria and ignore FLC results.
- c) In order to be classified as a hematologic response, confirmation of serum monoclonal protein, serum immunoglobulin free light chain (when primary determinant of response) and urine monoclonal protein (when primary determinant of

response) results must be made by verification on two consecutive determinations.

- d) Caution must be exercised to avoid rating progression or relapse on the basis of variation of radiological technique alone. Compression fracture does not exclude continued response and may not indicate progression. When progression is based on skeletal disease alone, it should be discussed with the PI before removing the patient from the study.

6.2.2 Evaluation of response Criteria by modified International Myeloma Working Group Criteria for Multiple Myeloma

a) Stringent Complete Response (sCR)

- Complete Response as defined below plus: Normal FLC ratio and absence of clonal cells in bone marrow by immunohistochemistry or immunofluorescence (presence/ absence of clonal cells is based on the kappa/ lambda ratio).

b) Complete Response (CR)

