- Negative immunofixation on the serum and urine and disappearance of any soft tissue plasmacytomas and $\leq 5\%$ plasma cells in bone marrow

c) Very Good Partial Response (VGPR)

- Serum and urine M-protein detectable by immunofixation but not on electrophoresis or 90% or greater reduction in serum M-protein plus urine M-protein level $< 100\text{mg}$ per 24h. If the serum and urine M-protein are unmeasurable, a $\geq 90\%$ decrease in the difference between involved and uninvolved FLC levels is required in place of the M-protein criteria.

d) Partial Response (PR)

- $\geq 50\%$ reduction in M protein and reduction in 24-h urinary M-protein by $\geq 90\%$ or to $< 200\text{ mg}$ per 24h. If the serum and urine M-protein are unmeasurable, a $\geq 50\%$ difference between involved and uninvolved FLC levels is required in place of the M-protein criteria

e) Minor Response (MR)

- $\geq 25\%$ but $\leq 49\%$ reduction of serum M protein and reduction in 24-hour urine M-protein by 50%-89%. In addition to this, if present at baseline, 25%-49% reduction in the size of soft tissue plasmacytomas is also required. No increase in size or number of lytic bone lesions (development of compression fracture does not exclude response)

f) Stable Disease (SD)

- Not meeting criteria for CR, VGPR, PR, MR or progressive disease. All categories also require no known evidence of progressive or new bone lesions if radiographic studies were performed. Radiographic studies are not required to satisfy these response requirements.

g) Progressive disease (PD)

- Requires any one or more of the following:
 - Increase of $\geq 25\%$ of best response and/or lowest measurable value in:
 - Serum M-component and/or (absolute increase must be $\geq 0.5\text{ g/dl}$.
The serum M-component increases of $\geq 1\text{ gm/dl}$ are sufficient to define

relapse if starting M-component is ≥ 5 gm/dl.

- Urine M-component and/or (the absolute increase must be ≥ 200 mg/24h
- Only in patients without measureable serum and urine M-protein levels: the difference between involved and uninvolved FLC levels. The absolute increase must be >10 mg/dl.
- Bone marrow plasma cell percentage: the absolute % must be $\geq 10\%$
- Definite development of new bone lesions or soft tissue plasmacytomas or definite increase in size of existing bone lesions or soft tissue plasmacytomas
- Development of that can be attributed solely to the plasma cell proliferative disorder

h) Relapse from CR:

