6.2.3 Duration of first Response

The duration of overall response is measured from the time measurement criteria are met for initial response until the first date that recurrent or progressive disease is objectively documented.

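### Biochemical progression is classified on one reading against the running lowest value, while response needs two consecutive readings; *confirmed* progression is never defined

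*Combined protocol and SAP*

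**What the plan says.** **Response.** Protocol 6.2.1(c) opens "In order to be classified as a hematologic response, confirmation of serum monoclonal protein" and, after extending the rule to free light chain (FLC) and urine M-protein where they are the primary determinant, closes "response) results must be made by verification on two consecutive determinations".

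**Progression.** Section 6.2.2(g) "Requires any one or more of the following". The biochemical criteria are a rise of at least 25% "of best response and/or lowest measurable value in" serum M-protein, urine M-protein or, where neither is measurable, the FLC difference. The serum item, "Serum M-component and/or (absolute increase must be" at least 0.5 g/dL, adds an absolute floor. No repeat reading is named. Section 6.2 assesses response on Day 1 of every cycle.

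**Consequences, in varying terms:**
- 5.11, discontinuation list: "Confirmed disease progression", followed by nearly the same criteria.
- 5.11, follow-up paragraph: "After documented disease progression each subject will be followed by telephone for overall survival".
- 6.2.3: duration of response runs "until the first date that recurrent or progressive disease is objectively documented".
- 8.1.2.1.1: confirmed progression moves the patient to survival follow-up.

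No section says what confirms progression. Sections 6.2.4 and 6.2.5 define PFS and TTP by progression to multiple myeloma, which is not the same term as PD in 6.2.2(g).

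**The concern.** The reference value in 6.2.2(g) is a running minimum. The lowest of several noisy readings lies below the true level, and it drifts lower as readings accumulate. Testing each new reading against it, without a repeat, gives a patient whose disease has not changed many chances to cross the threshold. Response is protected against a single aberrant reading; progression is not. Section 6.2.1(d) cautions against calling progression on radiological variation alone, but nothing comparable covers M-protein or FLC.

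The direct stake is whether a patient is classed as stable or progressive, and when a response is taken to have ended. The second stake is reproducibility. With *confirmed*, *documented*, *objectively documented* and no qualifier all in use, two assessors could give the same patient different PD status and dates. In a trial of 16 patients, a few such differences are visible in every summary.

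**Working it through.** The documents give no figure for misclassification or assay variability, so there is no stated value to reproduce. The check is a simulation.

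**Inputs from the protocol**
- PD on serum M-protein: rise of at least 25% and at least 0.5 g/dL over the lowest earlier value (6.2.2(g)).
- Readings: baseline plus 8 through cycle 8, nine in all, counting the pre-treatment and Cycle 1 Day 1 samples as one; 16 further cycles for patients who continue (2.1).
- Level: a spike of at least 3 g/dL is a listed risk factor (5.1.1), so 3.0 g/dL is a relevant stable value. On the serum component, 2.0 g/dL is a partial response from 4.0 or a minor response from 3.0; 1.5 g/dL is a partial response from 3.0.

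**Assumptions not in the protocol**
- Visit-to-visit CV of 3%, 5% or 7.5%.
- True level μ constant; errors normal and independent between visits.

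**Model.** Reading X_t = μ(1 + CV × Z_t), with Z_t standard normal. Let m be the lowest reading before t.
- One-reading PD: X_t ≥ 1.25m and X_t − m ≥ 0.5 for any t.
- Two-reading PD: X_t and X_(t+1) both meet both conditions against the same m.

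**Hand check at 3.0 g/dL.** For one pair of readings, PD needs X_2 − 1.25X_1 ≥ 0. The mean of that difference is 3.0 − 3.75 = −0.75, and its SD is 3.0 × CV × √(1 + 1.25²) = 4.80 × CV.
- CV 5%: SD 0.240, z = 3.12, probability 0.09%.
- CV 7.5%: SD 0.360, z = 2.08, probability 1.87%.

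Nine readings contain 9 × 8 / 2 = 36 ordered pairs, and one-reading PD occurs if any pair qualifies. The upper bounds are 36 × 0.09% = 3.2% and 36 × 1.87% = 67%. The simulated values below lie under them, as they should because pairs overlap.

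**Results: chance of at least one false serum PD, one reading → two readings**

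| True level and readings | CV 3% | CV 5% | CV 7.5% |
|---|---|---|---|
| 3.0 g/dL, baseline + 8 | 0% → 0% | 2.5% → 0.2% | 33% → 7% |
| 2.0 g/dL plateau, first reading + 16 | 0% → 0% | 2.2% → 0.1% | 46% → 8% |
| 1.5 g/dL plateau, first reading + 16 | 0% → 0% | 0.02% → 0% | 7.5% → 0.4% |

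If all 16 patients were stable at 3.0 g/dL, the first row means 16 × 0.025 = 0.4 false PD calls at CV 5% and 16 × 0.33 = 5.3 at CV 7.5%. Two readings bring these to 16 × 0.002 = 0.03 and 16 × 0.07 = 1.1.

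**Why the level matters.** Below a reference of 2.0 g/dL the 0.5 g/dL floor exceeds 25%; at 1.5 g/dL it demands 0.5 / 1.5 = 33%. At 1.0 g/dL over 8 cycles the one-reading risk is near zero up to CV 7.5%.

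**Second model.** With lognormal error and readings rounded to 0.1 g/dL, at 3.0 g/dL through cycle 8, the risks are 3.4% → 0.1% at CV 5%, 27.0% → 3.6% at CV 7% and 67.3% → 21.8% at CV 10%. The same model isolates the effect of the reference: at CV 7%, one reading judged against baseline only gives 7.9% instead of 27.0%.

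**Effect on the 8-cycle response rate.** A patient at a constant level never reaches partial response, so a false PD there cannot change the primary endpoint. For a patient falling linearly from 3.0 to 1.5 g/dL over 8 cycles, one-reading false PD is 0.01% at CV 5% and about 1.6% at CV 7.5%. For a late responder (flat for four cycles, then falling to 1.5) it is under 1% and 13%.

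**The case against.** **Removal from treatment needs confirmed progression.** This stands. A reader might infer that one high reading takes a patient off pembrolizumab and so costs responses in the primary endpoint. The documents do not say so: 5.11 and 8.1.2.1.1 both require confirmation. But the term is undefined, and it governs discontinuation and follow-up. It does not govern the classification in 6.2.2(g) or the date in 6.2.3.

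**TTP and PFS count progression to multiple myeloma.** This stands too. A reader might infer that false PD corrupts 30-month TTP, or that disease status is lost once follow-up moves to telephone. Section 4.1.4 ties freedom from progression to MM to current clinical guidelines. Note i of the study calendar keeps restaging scans and laboratory tests as clinically indicated after PD, and 8.1.2.1.1 has patients seen in clinic. TTP and PFS are exposed only if 6.2.2(g) is used to define their event.

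**A stable patient is not read 24 times on treatment.** Correct. Continuation past cycle 8 requires at least a minor response (2.1), so running a constant 3.0 g/dL over 24 cycles would describe a patient the protocol does not treat that long. The relevant long exposure is the responder on a plateau, shown above, where the floor gives partial protection.

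**The size rests on an unsupplied CV.** It does. At CV 3% the problem vanishes, and correlated errors would lower every figure. In the other direction, the urine, FLC and marrow criteria add chances that the simulation leaves out, and 6.1.2 admits results from outside laboratories.

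**The protocol cites published response criteria that might supply a rule.** That cannot be settled from the documents. Section 6.2.2 calls its criteria modified and writes them out, so its text is what assessors will apply.

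**Conclusion.** The asymmetry is real and goes beyond missing detail: applying 6.2.2(g) as written can classify unchanged disease as progressive. Over 8 cycles at a stable 3.0 g/dL the one-reading risk runs from 0% (CV 3%) to 33% (CV 7.5%), and a second reading cuts the latter to 7%. For responders on a plateau the risk depends strongly on level: at CV 7.5%, 46% at 2.0 g/dL but 7.5% at 1.5 g/dL. These figures assume the CV and independent errors, and they cover the serum criterion only.

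The direct effect is on stable/progressive classification and duration of response. An effect on the 8-cycle response rate arises only if *confirmed* is read loosely and a late responder is stopped early. An effect on TTP or PFS arises only if 6.2.2(g) is taken to define progression to multiple myeloma. The point should be corrected, but it does not undermine the design.

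**What to change.** **For endpoint classification (6.2.2(g) and 6.2.3):** state that PD based on serum M-protein, urine M-protein or FLC must be met on two consecutive determinations against the same reference value, and is dated to the first of them. This mirrors 6.2.1(c).

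**For the other sections:** define *confirmed* once, and reconcile the wording of 5.11 (both paragraphs), 6.2.2(g), 6.2.3 and 8.1.2.1.1. State whether PD under 6.2.2(g) is the event counted in 6.2.4 and 6.2.5. What should lead to stopping treatment is for the sponsor and investigator to settle; this point asks only that the passages agree.

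**Cost:** protocol wording. On treatment the next Day 1 sample is already scheduled, so biochemical PD is classified one reading later with its date unchanged. Off treatment the minimum schedule is every 6 to 12 months (study calendar, note i), so a repeat sample may have to be arranged. The rule reduces the risk without removing it: at 3.0 g/dL over 8 cycles and CV 10%, the second model above still gives 21.8% with two readings.

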6.2.3 Duration of first Response

The duration of overall response is measured from the time measurement criteria are met for initial response until the first date that recurrent or progressive disease is objectively documented.

6.2.4 Progression-Free Survival

PFS is defined as time of start of treatment to time of progression to multiple myeloma or death, whichever occurs first.

6.2.5 Time to progression

TTP is defined as time of start of treatment to time of progression to multiple myeloma.

6.2.5.1 Overall Survival

Overall survival is defined as the time of start of treatment to death from any cause.

6.2.6 Overall response rates after 8 and 24 cycles of treatment

Overall response rates (ORR) is PR+VGPR+CR+sCR.

6.2.7 Clinical Benefit Rate after 8 and 24 cycles of treatment

Clinical benefit rate (CBR) is sCR+CR+VGPR+PR+MR.

7.0 STUDY CALENDAR

Study	Pre-Treatment	Initial treatment			Disease progression at any time point ^j	Follow Up ^{i,j}
		Cycle 1 ^k	Cycles 2-24 ^k			
		Day 1	Day 1	End of Cycle 8/ end of Cycle 24		
Medical Record Review	X					
H&P	X	X	X	X	X	X
ECOG	X	X	X	X	X	X
Informed Consent	X					
EKG	X					
Routine Labs ^a	X	X	X	X	X	X
24 hour urine for UPEP and IFE ^m	X		X	X	X	X
Viral Studies ^b	X					
Pregnancy Test ^{c,d,e}	X ^c	X	X ^c			
Myeloma tests ^f	X	X	X	X	X	X
Research Blood/Urine	X		X	X	X	X
Bone Marrow/Aspirate	X ^g			X ^h	X ^h	X ^m
FDG PET-CT	X ^m			X ^m	X ^m	X ^m
Skeletal Survey	X			X	X	X ^m
MRI of the thoracic and lumbar spine	X ^m			X ^m	X ^m	X ^m
Pembrolizumab		X	X			
Adverse Events/Toxicity			X	X	X	X
Concomitant Medications ⁿ	X				X	

- Routine tests include CBC with differential, chemistry panel, liver function tests (AST, ALT, ALK and total bilirubin), amylase, lipase, TSH, T4, uric acid, eGFR determination and LDH. PT and PTT will only be performed at baseline. Reticulocyte count will only be performed at baseline.
- Viral studies include HIV, Hep B surface antigen and Hep C antibody. If Hep C antibody positive, Hep C RNA PCR will be performed

- c. Pregnancy tests (urine or serum) for females of childbearing potential. A female of childbearing potential (FCBP) is a sexually mature female who: 1) has not undergone a hysterectomy or bilateral oophorectomy; or 2) has not been naturally postmenopausal for at least 12 consecutive months (i.e., has had menses at any time in the preceding 12 consecutive months)
- d. Pregnancy tests (urine or serum) must occur within 10 – 14 days and again within 24 hours prior to prescribing pembrolizumab for Cycle 1
- e. FCBP with regular or no menstruation must have a pregnancy test (serum or urine) weekly for the first 28 days and then every 28 days while on therapy (including breaks in therapy); at discontinuation of pembrolizumab and at Day 28 post the last dose of pembrolizumab. Females with irregular menstruation must have a pregnancy test (serum or urine) weekly for the first 28 days and then every 14 days while on therapy (including breaks in therapy), at discontinuation of pembrolizumab and at Day 14 and Day 28 post the last dose of pembrolizumab.
- f. Myeloma tests include serum protein electrophoresis, serum immunofixation, 24 hour urine electrophoresis and urine immunofixation, serum free light chains, quantitative immunoglobulins, beta-2 microglobulin.
- g. Baseline bone marrow aspiration and biopsy will be sent to Department of Pathology, flow cytometry, FISH/cytogenetics, multiple myeloma tissue bank, gene expression profiling, whole exome sequencing, VDJ sequencing and storage.
- h. Bone marrow aspirate and biopsy can be performed +/- 21 days of intended cycle day. Bone marrow aspirate and biopsy will be sent to Department of Pathology, flow cytometry, FISH/cytogenetics, gene expression profiling, VDJ sequencing and storage.
- i. At minimum, follow-up will be every 6-12 months until progression of disease, institution of alternative therapy, or death. Patients may be followed at more frequent time intervals if clinically indicated, ie following post-therapy toxicity. Patients who have progressive disease while on study will be followed with restaging scans and laboratory tests as clinically indicated. Patients who are taken off treatment will continue to be followed for survival by phone or clinic visit.
- j. Variations of +/- 14 days of scheduled visits are permitted.
- k. Variations of +/- 3 days of scheduled visits are permitted.
- l. Peripheral blood sample only.
- m. If clinically indicated
- n. All concomitant medications received within 28 days before the first dose of trial treatment and 30 days after the last dose of trial treatment should be recorded in the medical record.

8.0 TRIAL PROCEDURES

8.1.1 Administrative Procedures

8.1.1.1 Informed Consent

The Investigator must obtain documented consent from each potential subject prior to participating in a clinical trial.

Consent must be documented by the subject's dated signature or by the subject's legally acceptable representative's dated signature on a consent form along with the dated signature of the person conducting the consent discussion.

A copy of the signed and dated consent form should be given to the subject before participation in the trial.

The initial informed consent form, any subsequent revised written informed consent form and any written information provided to the subject must receive the IRB approval/favorable opinion in advance of use. The subject or his/her legally acceptable representative should be informed in a timely manner if new information becomes available that may be relevant to the subject's willingness to continue participation in the trial. The communication of this information will be provided and documented via a revised consent form or addendum to the original consent form that captures the subject's dated signature or by the subject's legally acceptable representative's dated signature.

Specifics about a trial and the trial population will be added to the consent form template at the protocol level.

The informed consent will adhere to IRB requirements, applicable laws and regulations and Sponsor requirements.

8.1.1.2 Adverse Event (AE) Monitoring

The investigator or qualified designee will assess each subject to evaluate for potential new or worsening AEs as specified in the study calendar and more frequently if clinically indicated. Adverse experiences will be graded and recorded throughout the study and during the follow-up period according to NCI CTCAE Version 4.0. Toxicities will be characterized in terms regarding seriousness, causality, toxicity grading, and action taken with regard to trial treatment.

For subjects receiving treatment with pembrolizumab all AEs of unknown etiology associated with pembrolizumab exposure should be evaluated to determine if it is possibly an event of clinical interest (ECI) of a potentially immunologic etiology (termed immune-related adverse events, or irAEs); see the separate ECI guidance document in Appendices (Section 12.0) regarding the identification, evaluation and management of potential irAEs.

